Posttraumatic stress disorder (PTSD) is a psychiatric disorder that occurs in response to certain traumatic experiences (TE). The fifth edition of the Diagnostic and Statistical Manual of Mental Disorders (DSM-5) defines a TE for purposes of PTSD as exposure to - actual or threatened death, serious injury or sexual violence. The exposure may be direct, or may be indirect (witnessing the event, learning of the event occurring to a loved one, or repetitive confrontation with aversive details of such an event – usually in the course of professional duties). PTSD is characterized by responding to the TE by persistently re-experiencing it, avoiding thoughts or reminders of it, having new negative thoughts or feelings, becoming more aroused and reactive, and experiencing distress or functional impairment (e.g., socially or professionally). To meet diagnostic criterion, the symptoms may not be due to medication, substance abuse, or other illness. The DSM-5 recognizes two specifications for this disorder, a delayed onset subgroup, where full diagnostic criteria are not met until 6 or more months after the TE, and a subgroup that experiences high levels of dissociation, either through depersonalization ("not happening to me") or derealization ("things are not real"). (American Psychiatric Association, 2013). Evidence for the existence of this highly symptomatic dissociative subgroup was buttressed by Wolf et. al. using latent class analysis, appearing to be highly specific to TEs involving sexual assault both in children and adults. (Wolf, et al., 2012)

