Lifetime prevalence of PTSD is estimated at 5 to 8% of men and 10 to 14% of women, making it one of the most common psychiatric disorders. (Breslau, et al., 1991) (Kessler, et al., 1995) (Yehuda, et al., 2002) (Kilpatrick, et al., 2013) Breslau et.al. estimate that it affects 15-24% of people exposed to a traumatic event. (Bresslau, et al., 2001a) Yehuda et. al. report that 55% of rape victims develop PTSD. (Yehuda, et al., 2002) In addition, large numbers of service members develop PTSD following combat exposure. In a survey of members of the National Guard following combat in Iraq, 23.4% developed PTSD with some functional impairment, and 8.9% developed PTSD with serious functional impairment. (Thomas, et. al., 2010)

To explore the epidemiology of traumatic events, Kilpatrick et. al. studied a sample of 2953 U.S. adults recruited online who then completed an assessment using the National Stressful Events Survey, a structured self-administered survey. Of these, 89.7% reported exposure to at least one DSM-5 criterion TE type; where the modal number of such TE types experienced was 3 (mean=3.3, SD-2.32), and at least 30% of the sample experienced 6. In addition to the majority of participants reporting multiple events, many were exposed to more than one type of TE. Percentages reported were: (1) disaster 50.5%, (2) accident/fire 48.3%, (3) exposure to hazardous chemicals 16.7%, (4) combat or warzone exposure 7.8%, (5) physical or sexual assault 53.1%, (6) witnessed physical/sexual assault 33.2%, (7) witnessed dead bodies/parts unexpectedly 22.6%, (8) threat of injury to family or close friend due to violence/accident/disaster 32,4%, (9) death of family/close friend due to violence/accident/disaster 51.8%, and (10) work exposure 11.5%. The prevalence of sexual assault as a separate category was 29.7% overall, where women reported 42.4% and men reported 15.8% exposure. (Kilpatrick, et al., 2013) Benjet et al. reported international results of the World Mental Health Survey Consortium in a 24-country cohort of 68,894 adults where 29 types of TE and their interrelationships were examined. (Benjet, et al., 2016) This study also supports the observation that exposure to TEs is nearly omnipresent, and the majority of TE experiencers are exposed to multiple TEs. The authors indicate that further research is required to illuminate the mechanisms accounting for associations of prior TEs with subsequent TEs.

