All subjects who finish BL assessments and meet inclusion/exclusion criteria will be randomized into one of two groups, "Active eTMS" and "Sham eTMS", in a 1:1 ratio, stratified by clinic. Stage 2 will consist of a randomized period and an open-label period. During the randomized period, the Active eTMS group will receive Active eTMS and the Sham eTMS group will receive Sham eTMS twice per day, with 20 total treatments delivered in a 2 or 3-week period. Following the randomized period of the study, all Sham eTMS subjects will have the option of participating in the open-label portion of the study. Those who choose to participate in open-label treatment will receive 20 Active eTMS sessions, twice per day, which must be completed in a period of 21 calendar days.

All groups will undergo an assessment of symptoms at baseline, before Week 6 (F1), and then again at the end of Week 10 (F2). The primary efficacy endpoint, and outcome time point, is Wave Neuroscience, Inc. Protocol eTMS-PTSD Rev 1.1 11 January 2024 PAGE 28 change in Post-Traumatic Stress Disorder symptoms between the Baseline (BL) and the first follow-up (F1). The primary efficacy outcome will be measured using the PCL-5. Safety outcomes will be measured by recording adverse events, incidence and type.

PARTICIPANT POPULATION

The enrollment goal for the combined two stages of the study is 170 participants of any gender or ethnic background, age 22-65 years, with Post-Traumatic Stress Disorder. Thirty (30) participants will be part of Stage 1 and be provided with open-label treatment to evaluate safety of eTMS in this population. 140 participants will be part of Stage 2, randomized to either active or sham eTMS, in a 1:1 allocation ratio, stratified by recruitment site. Participants randomized to sham eTMS in Stage 2 will receive an additional series of open-label active eTMS following the randomized portion of Stage 2.

Inclusion Criteria

Participants must meet all following inclusion criteria to qualify for enrollment into the study:

- 1. Willing and able to consent to participate in the study via signed Informed Consent
- 2. Age 22 65 years
- 3. Provisional diagnosis of PTSD according to Veterans Administration PCL-5 rubric fulfillment AND cutpoint score of 31 or above
- 4. Positive identification as either a Veteran, or First Responder (e.g., emergency medical service provider, firefighter, or any other emergency response personnel)

Exclusion Criteria

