- 3. The F1 EEG may serve as the treatment-setting EEG for the Open Label period if treatment begins within 15 days of the collection of the F1 EEG. Otherwise, conduct another EEG within 15 days of the first Open Label treatment

Data to be collected

The data to be collected include, according to the schedule in the Schedules of Activities, above, include:

- DSM-5 PTSD Checklist (PCL-5)
- Veterans RAND 36-Item Health Survey(VR-36)
- TMS Screening Form (TMSs)
- Mini Mental Status Exam (MMSE)
- Columbia Suicide Severity Rating Scale (CSSRS)
- Ohio State University Traumatic Brain Injury Identification Method (OSU-TBI-ID)
- Drug History Questionnaire (DHQ)
- Life Events Checklist for DSM-5 (LEC-5)
- Clinical Global Impression (CGI)
- Computerized Neuropsychological Battery (Braincheck)
- Somatic Symptom, Anxiety, Depression Screen (PHQ-SADS)
- Alcohol Use Disorders ID Test (AUDIT)
- Morphine Equivalent Dose (MED)
- Opiate Craving Scale (OCS)
- Drug Abuse Screening Test (DAST-10)
- Pittsburgh Sleep Quality Index (PSQI) •
- Side Effects Questionnaire (SEQ)
- EEG/ECG •
- Brief Pain Inventory (BPI)
- Blinding Assessment
- Body Temperature
- Blood Pressure
- Concomitant treatments: background supportive, physical, and neuromodulatory
- Concomitant medications
- Concomitant illicit drug use
- Concomitant alcohol use
- Adverse Events
- Demographics/Military/First Responder
- Medical/Psychiatric History
- Pregnancy

PCL-5: The PCL-5 is a measure of severity of PTSD symptoms. . The PTSD Checklist-5 is a 20item self-report measure that assesses the 20 DSM-5 symptoms of PTSD. The PCL-5 has a variety of purposes including monitoring symptom change during and after treatment, screening individuals for PTSD, and making a provisional PTSD diagnosis. Each item ranges from 0 to 4 (0=not at all, 1=a little bit, 2=moderately, 3=quite a bit, 4=extremely), and a total score ranging from 0 to 80. It takes approximately 5 - 10 minutes to complete. It can be administered in 3 formats: without Criterion A (TE exposure), with a brief Criterion A assessment, or with the Life Events Checklist for DSM-5 (LEC-5) and extended Criterion A assessment. When used for provisional diagnosis, instead of for severity measurement, the DSM-5 diagnostic rubric is followed to assure distribution across the symptom clusters, but when other diagnostic measures Wave Neuroscience, Inc. Protocol eTMS-PTSD Rev 1.1 11 January 2024

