provide the diagnosis (i.e., the CAPS-5), a simple summation of severity scores across the 20 items may be used to determine probable PTSD. Initial research indicates that a cut off score of between 31 and 33 signals probable PTSD. (U.S. Department of Veterans Affairs, 2022) (Spoont, et al., 2013) A provisional PTSD diagnosis can be made by treating each item rated as 2 = "Moderately" or higher as a symptom endorsed, then following the DSM-5 diagnostic rule which requires at least: 1 B item (questions 1-5), 1 C item (questions 6-7), 2 D items (questions 8-14), 2 E items (questions 15-20). In order to avoid enrolling persons who do not have PTSD, criteria for the diagnostic rubric must be fulfilled AND a minimum PCL-5 score of 31 will be required. Evidence for the PCL for DSM-IV suggests that a 5-10 point change represents reliable change and a 10-20 point change represents clinically significant change. It is recommended to use 10 points of change as a minimum threshold for determining whether the improvement is clinically meaningful. Change score characteristics are currently being determined regarding reliable and clinically meaningful change. The VA recommends following the DSM-IV recommendations. The PCL-5 is the primary efficacy outcome for Stage 2 of this trial. Morrison et. al., in the first study on the PCL-5's psychometric properties for first responders in the United States, studied a sample of 133 first responders, including firefighters/EMT (76.7%) and police (23.3%). The mean total PCL-5 score was 38.73 (SD = 18.68, range 0-72). (Morrison, Su, Keck, & Beidel, 2021)

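### Eligibility requires PTSD symptoms but no qualifying traumatic event, although LEC-5 collects event history at baseline before eligibility is decided

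*Combined protocol and SAP*

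**What the plan says.** **Definition.** The Introduction (Post-Traumatic Stress Disorder) presents PTSD as a disorder arising from traumatic experience (TE). It says that DSM-5 "defines a TE for purposes of PTSD as exposure to - actual or threatened death, serious injury or sexual violence".

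**Eligibility rule.** Inclusion criterion 3, in the Synopsis and under Participant Population, reads "Provisional diagnosis of PTSD according to Veterans Administration PCL-5 rubric fulfillment AND cutpoint score of 31 or above". The PCL-5 entry under Data to be collected spells the rubric out. An item counts when rated 2 or higher, and the candidate must meet the "DSM-5 diagnostic rule which requires at least: 1 B item (questions 1-5), 1 C item (questions 6-7), 2 D items" and two E items. There is no A item. The same entry states the purpose of the double requirement: "In order to avoid enrolling persons who do not have PTSD, criteria for the diagnostic rubric must be fulfilled AND a minimum PCL-5 score". That minimum is the cutpoint of 31.

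**Format.** The PCL-5 entry says: "It can be administered in 3 formats: without Criterion A (TE exposure), with a brief Criterion A assessment, or with the Life Events Checklist" and an extended Criterion A assessment. It does not say which format this trial uses.

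**Event data.** Tables 4 and 5 schedule LEC-5 at baseline (BL) in both stages. Its description covers lifetime exposure to 17 event types, how the person was involved, and whether life was threatened or serious injury occurred. Baseline Visit and Eligibility Determination places the eligibility decision after the BL procedures. Study Design (Stage 2) then randomises everyone who completes BL and meets the criteria.

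**The concern.** By the protocol's own definition, a person with no qualifying event does not have PTSD, whatever the PCL-5 total. The rule that is meant to keep such people out tests symptoms only. The information that would close the gap is collected in time, but nothing in the criteria refers to it.

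Two things are at stake. The first is the label: the objective is efficacy in PTSD, and without an event requirement the enrolled sample cannot be shown to meet the protocol's own definition. The second is dilution: if eTMS acts on PTSD specifically, participants without it would pull the mean difference towards zero.

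**Working it through.** **1. Search for an event requirement.** None of the four inclusion or fifteen exclusion criteria mentions a traumatic event. Inclusion 4 requires Veteran or First Responder status, which is an occupation and not an exposure. The LEC-5 entry describes the instrument as a preliminary to CAPS-5, but Tables 4 and 5 schedule neither CAPS-5 nor any other PTSD diagnostic interview. By contrast, Suicidality and Harm to Others gives explicit C-SSRS thresholds for ineligibility. The protocol writes such rules where it intends them.

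**2. Who can pass.** PCL-5 items score 0 to 4. B has 5 items, C has 2, D has 7 and E has 6.
- Smallest total that satisfies the rubric: (1 + 1 + 2 + 2) × 2 = 12. The cutpoint of 31 therefore adds a real restriction.
- Largest total from D and E alone: 13 × 4 = 52. This exceeds 31 but fails the rubric, because no B or C item is endorsed.
- Smallest B and C contribution that passes: 2 + 2 = 4. The other 31 − 4 = 27 points can come from D and E.

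So the person at issue endorses at least one B item and one C item at moderate level, meets the D and E counts, reaches 31, and has no qualifying event. No written rule stops that person.

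**3. The plan's power figure.** Sample Size Considerations for Stage 2 gives a difference of 15, SD 18.68, 54 completers per group, two-sided alpha 0.05 and power 0.985. For a two-sample t-test the noncentrality is λ = δ / (SD × √(2/n)) with 2n − 2 = 106 degrees of freedom. With δ = 15, λ = 15 / (18.68 × √(2/54)) = 4.17, and power is 0.9852. The stated figure reproduces. So does the randomised number: 108 / 0.9 = 120.

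**4. Dilution.** Let f be the fraction without a qualifying event. Assume that they gain nothing over sham and that the SD is unchanged, so δ = 15(1 − f). The documents do not give f for this population. The only related figure in the Introduction comes from 2,953 US adults recruited online, of whom "89.7% reported exposure to at least one DSM-5 criterion TE type", leaving 10.3% without one.

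| f | Number of 120 | δ | Power, 54 per group |
|---|---|---|---|
| 0 | 0 | 15 | 0.985 |
| 2% | 2.4 | 14.7 | 0.982 |
| 5% | 6 | 14.25 | 0.975 |
| 10% | 12 | 13.5 | 0.961 |
| 10.3% | 12.4 | 13.455 | 0.960 |

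At the final-analysis level of 0.049, power for f = 10.3% is 0.959. Study Design states 126 completers instead of 108. With 63 per group, power goes from 0.994 at f = 0 to 0.980 at f = 10.3%.

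For a true difference of 10, which is not the design value, power with 54 per group is 0.787, 0.745 and 0.699 at f = 0, 5% and 10%. Most of the shortfall from 0.985 comes from the smaller effect, not from eligibility.

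**The case against.** The strongest defence has four parts.

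- **The rubric is not a bare symptom count.** A reader might infer that 31 points of depression, anxiety or brain-injury symptoms are enough. They are not: step 2 shows that D and E symptoms alone fail at any total. This stands, and it narrows the group considerably. It does not empty it, because endorsing a B and a C item does not establish that a qualifying event occurred.
- **There are backstops.** A reader might infer that the LEC-5 result can play no part. The documents do not say that. Baseline results are reviewed before eligibility is decided, the site Investigator signs a checklist with supporting materials, and exclusion 15 allows judgement about conditions that limit interpretation. Scheduling LEC-5 beside the PCL-5 also suggests that the Criterion A format may be intended. But these routes are discretionary, and up to three sites may be added in Stage 2, so practice could differ between sites.
- **The diagnosis is called provisional.** The protocol discusses at length how loosely or strictly PTSD may be defined, and rubric plus cutpoint is stricter than either alone. That is fair. The stated purpose of the rule is nevertheless to keep out people without PTSD, and the objective is framed as treatment of PTSD.
- **An event rule would exclude few people.** This is probably true. A lifetime event also does not prove that current symptoms arise from it. The Introduction further reports that multiple exposure is the norm and that a single-event criterion is unrealistic. This argues against tying ratings to one index event, and the fix respects it. The Introduction also reports that narrower DSM-5 event rules were one of two main reasons why DSM-IV cases failed DSM-5, so event qualification does affect who counts as a case.

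**Conclusion.** The gap is real: the written criteria allow randomisation of people whom the protocol's own definition would not call PTSD cases, while the data needed to identify them are already collected.

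Its practical size is probably small. The 0% to 10% range is an assumption. Its upper end comes from general adults, not from Veterans or First Responders who also meet the rubric and the cutpoint, so the true share is plausibly lower. Zero benefit in every such participant is also an assumption. Under both, power at the planned difference stays at about 96% or more.

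A reader might infer that the trial is underpowered or that the active-sham comparison is biased. Neither follows. The planned power survives, and randomisation protects the comparison whatever the case mix. What is weakened is the statement of whom the result applies to. The change is worth making because it is cheap and answers the protocol's own stated aim.

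**What to change.** 1. In inclusion criterion 3 (Synopsis and Participant Population), add: *and at least one DSM-5 Criterion A event (one or more) documented on the BL LEC-5*.
2. Add the same item to the eligibility checklist described under Baseline Visit and Eligibility Determination.
3. In the PCL-5 entry, state that the LEC-5/Criterion A format is used, with the same event or set of events as reference at BL and F1, and that no single index event is required.

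**Cost.** One criterion line, one checklist item and one sentence on format. No new instrument or visit is needed, and no stated sample size or power figure changes. The downside is a few more screen failures.

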FDA has cleared rTMS for major depressive disorder. rTMS is a noninvasive method to cause depolarization or hyperpolarization of neurons in the brain. It uses electromagnetic induction to induce weak electric currents using a rapidly changing magnetic field; this can cause activity in specific or general parts of the brain with minimal discomfort, allowing the functioning and interconnections of the brain to be studied. Most rTMS treatment protocols are carried out with unified stimulation parameters, such as dorsolateral left prefrontal cortex (DLPFC) stimulation for patients with major depressive disorder using a10 Hz repetitive pulse at 120% of motor threshold (MT), 5 days a week for 6 weeks. (See **Table 1** below) A variety of TMS protocols have been tested as a treatment tool for various neurological and psychiatric disorders including migraine, stroke, Parkinson's disease, dystonia, tinnitus, depression, and auditory hallucination. Mayer et al. concludes that some participants may derive long-term benefit from the rTMS course. (Mayer, Aviram, Walter, Levkovitz, & Bloch, 2012) However, there is a lack of clinical trials to show the safety and efficacy of rTMS in persons with PTSD.

The rTMS system to be used in this study has been shown to have an excellent safety profile, with nearly all adverse events being minor. In a review (Janicak, et al., 2008) of three rTMS studies involving 325 patients, no serious adverse event was reported that was due to the rTMS treatment. During acute treatment, the most common adverse event was headache, reported in 58.2% of active and 55.1% of sham groups. Headache was assessed by the study investigator as "severe" in 4.2% of active TMS and 5.1% of sham groups. Transient headache, which resolves spontaneously or with mild analgesics, is the most common adverse effect of rTMS in adults. Site pain was reported by 35.8% in active TMS group and 3.8% in the sham group. Pain was reported as "severe" in 6.1% of active and none in the sham. All other adverse events were very infrequent across all groups. The eTMS protocol is conducted at 50% MT, unlike the standard rTMS 10 Hz protocol, which is conducted at 120% MT. Reduction of % MT intensity reduces site pain. Intensity is reduced when using eTMS protocols when a participant indicates discomfort at the starting intensity of 50% MT. No serious adverse event occurred during the pilot phase of a sister trial to this trial (MeRT-005).

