A randomized, double-blind sham-controlled trial of veterans with PTSD was conducted by Sponsor's predecessor. Data from the preliminary dataset are available. Eighty-six (86) participants were randomized to MeRT or Sham MeRT. After completion of phase 1, the randomized, blinded portion of the study, participants continued to be treated, unblinded, with active MeRT for an additional two weeks in phase 2. The Per Protocol (PP) data analysis set consisted of 80 participants; 6 (3 Sham MeRT-treated, 3 MeRT-treated) were removed from the intent to treat analysis population for protocol deviations, such as incomplete study treatment or data collection, or medical issues. All removals were determined prior to unblinding the decision makers. As displayed in **Figure 1**, below, the MeRT-treated group showed a statistically significantly higher therapeutic effect than the Sham-treated group in the double-blind phase. Symptom reduction as measured by mean percentage PCL-M score reduction of 46% in the MeRT-treated group was significantly greater than 30% reduction in the Sham MeRT-treated group at week 2 (2-tailed t-test; p = 0.017). The proportion of participants who had a 30% or greater reduction from the Screening Visit to week 2 was significantly different in the MeRT-treated versus Sham MeRT-treated group (74.5% versus 40%, respectively, 2-tailed z-test of proportions p=0.007).

In the unblinded phase, both groups continued to show clinical improvement. The PCL-M reductions, and percentage reductions in the two groups were almost identical at week 4 (Sham=31.7, MeRT=32.5, and Sham=63.9%, MeRT=66.8%; respectively). The average PCL-M score percentage reduction over the 4-week treatment for the aggregate of both groups was 65.4%.

STUDY OBJECTIVE

The primary objective of the eTMS-PTSD-001 trial is to evaluate the safety and efficacy of electroencephalogram (EEG) personalized transcranial magnetic stimulation (eTMS) for the treatment of Post-Traumatic Stress Disorder (PTSD).

Wave Neuroscience, Inc. Protocol eTMS-PTSD Rev 1.1 11 January 2024

STUDY DESIGN

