This study is randomized, double-blind, and sham-controlled. It is not triple-blind, i.e., the treating technician/coordinator will know the participant's study assignment. Participants, Investigators and assessors will be blind to treatment assignment. Specifically, no primary or secondary outcome data will be collected by, or seen by, the unblinded technician/coordinator. Additionally, exploratory outcomes will be self-administered with electronic data capture, and also will not be seen or collected by unblinded personnel. The technician/coordinator will have reduced contact with participants in comparison to Sponsor's previous eTMS clinical trials, due to increased remote data collection (also leading to reduced dwell time at the clinic), and barrier separation from technicians during as much of the EEG/ECG and treatment procedures as is physically possible.

Blinding challenges arise from visual, aural, and proprioceptive sources. Unless the connection of the coil assembly to the stimulator is hidden from the participant, the participant will know if the coil used is or is not properly engaged with the stimulator. The discharging coil head produces a clicking sound at the frequency of discharge that is audible to the participant. Additionally, the discharge of the coil head on the forehead is accompanied by a tapping sensation, sometimes strong enough to produce discomfort. The Test Phase of this trial relies on a combination of visual barriers and exclusion of persons who have in the past received any form of rTMS treatment to accomplish blinding of the participant.

Visual blinding is accomplished by concealing the stimulator end of the coil assembly. Two coils are attached to the stimulator, but only one of them is engaged properly with the stimulator so as to produce magnetic discharges at the coil head. The other is merely taped or tied in place for stability. The engaged coil is held to the forehead of active-assigned participants and the unengaged coil is held to the forehead of sham-assigned participants. The coil to be used with the participant is threaded through a barrier sufficient to hide whether the stimulator connection part of the assembly is engaged with the stimulator or merely tied down nearby.

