CGI: The CGI is a clinician-rated instrument that evaluates symptom severity (CGI-S), whether and what direction treatment response takes (CGI-I), and relative efficacy vs. side effects of treatment (CGI-E). The CGI-S provides a rating of mental illness severity on a 7-point Likert scale (1- normal, 2- borderline, 3- mildly ill, 4- moderately ill, 5- markedly ill, 6- severely ill, 7extremely ill). The CGI-I describes change in mental illness with respect to baseline and due to treatment on a 7-point Likert scale (1- very much improved, 2- much improved 3- minimally improved, 4- no change, 5- minimally worse, 6- much worse, 7- very much worse). The CGI-E indicates a combination of therapeutic effect (marked improvement, moderate improvement, minimal improvement, unchanged or worse) and severity of side effects experienced (none, not functionally significant, functionally significant, outweighs therapeutic effect) on a 16-point scale.

Braincheck: Braincheck is a computerized, repeatable, neurocognitive test battery composed of well-known neuropsychological tests. It includes immediate and delayed recognition tests, tests of visual search speed, scanning, processing speed, mental flexibility, and executive functioning. Specific tests include trail marking, digit-symbol substitution tests, Stroop color, and word tests. Administration takes 15 minutes on average.

PHQ-SADS: The PHQ-SADS is a combination of the PHQ-9, PHQ-15, GAD-7 and the first five items of the PHQ panic module. It was developed based on observations of commonly occurring comorbidity between depression, anxiety, and somatization. Respondents are asked to consider the frequency of symptoms experienced over the past two weeks (PHQ-9 and GAD-7) or four weeks (PHQ-15). Administration takes approximately 10 minutes. Scores are based on thresholds for the individual component scales: scores of 5 (mild), 10 (moderate) and 15 (severe or moderately severe).

AUDIT: The AUDIT is a 10-item self-report questionnaire that provides information about habits surrounding alcohol use, including alcohol consumption, drinking behavior and alcohol-related problems. Each question is scored from 0-4 points. Administration time is 5 minutes. The total score ranges from 0-40, with higher scores being more concerning for unsafe drinking habits. A total score of 8 or more identifies individuals at risk for alcohol use disorder.

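### Read literally, the CGI-I definition makes a blinded rater attribute change to treatment, so a guess about the arm can enter the score

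*Combined protocol and SAP*

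**What the plan says.** Under Data to be collected, the CGI is described as clinician-rated, with three parts. CGI-S rates current severity. For improvement, "The CGI-I describes change in mental illness with respect to baseline and due to treatment", on seven anchors that run from very much improved to very much worse and mention only change. CGI-E "indicates a combination of therapeutic effect" and side-effect severity. No section tells the rater to score total change irrespective of cause.

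On blinding, the protocol states that "Participants, Investigators and assessors will be blind to treatment assignment". The synopsis (Study Treatment Regimen: Stage 2 Randomized) says the disconnected coil produces no magnetic field and the sham participant gets no treatment. The Blinding section adds that the tapping sensation of active stimulation will be missing under sham. It also says that "exploratory outcomes will be self-administered with electronic data capture", which does not fit a clinician-rated scale.

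Table 5 schedules the CGI at baseline, F1, F2 and F3, with the side-effects questionnaire and adverse events collected at the same visits. The CGI is not named as a primary or safety outcome; the primary efficacy outcome is the self-reported PCL-5.

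**The concern.** The definition sets two conditions: that the participant has changed, and that treatment caused the change. Attribution is the question the randomised comparison is there to answer. If the rater answers it participant by participant, belief about allocation becomes part of the measurement. Two people with the same improvement could be scored differently because one is thought to have had sham.

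If the belief is unrelated to the true arm, this only adds noise. If it tracks the arm, it produces a difference in favour of active treatment. Cues that could make it track the arm exist: a participant may mention the tapping sensation, and CGI-E asks the same clinician to grade side effects. Blinding assessment is listed only among participant-reported outcomes, and no rater guess is described, so the accuracy of raters' beliefs could not be checked afterwards.

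What is at stake is the credibility of CGI-I as clinician-rated support for a self-reported primary outcome.

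**Working it through.** **The plan's own figure.** The only design calculation is for the PCL-5: difference 15, SD 18.68, 54 completers per group, two-sided 5%. The noncentrality is 15 / (18.68 × √(2/54)) = 4.17, and the t-test power is 0.985, as stated. Nothing below changes it. CGI-I has no sample size, effect size or alpha in the documents.

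**Inputs to the illustration.**
- n = 54 per arm (Sample size considerations for Stage 2).
- Two-sided 5% (same section).
- 40% improve in both arms, so there is no true effect. This borrows the sham rate of at least 30% PCL-M reduction in the sponsor's predecessor's trial (Preliminary Data: "74.5% versus 40%, respectively, 2-tailed z-test of proportions p=0.007"). Using it for CGI-I is an assumption.
- q = probability that the rater's belief about the arm is right, the same in both arms (assumed).
- c = share of improvers believed to be on sham who are still rated improved (assumed). c = 1 means beliefs do not affect the score.

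**Formulas.**
- P(rated improved, active) = 0.40 × [q + c(1 − q)]
- P(rated improved, sham) = 0.40 × [(1 − q) + cq]
- Spurious difference = 0.40 × (1 − c)(2q − 1)

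Example, q = 0.7 and c = 0.5: active 0.40 × (0.70 + 0.15) = 34%; sham 0.40 × (0.30 + 0.35) = 26%; difference 8 points.

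**Results.** Rated improved, active v sham, and the false-positive rate of a two-proportion z-test by exact binomial enumeration:

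| Guess accuracy q | c = 0.75 | c = 0.5 | c = 0 (upper bound) |
|---|---|---|---|
| 50% | 35% v 35%; 5% | 30% v 30%; 5% | 20% v 20%; 5% |
| 60% | 36% v 34%; 6% | 32% v 28%; 7% | 24% v 16%; 18% |
| 70% | 37% v 33%; 7% | 34% v 26%; 15% | 28% v 12%; 56% |
| 80% | 38% v 32%; 10% | 36% v 24%; 27% | 32% v 8%; 90% |

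**A second model.** Treat CGI-I as a mean score, with the rating shifted by s points between believed-active and believed-sham. The spurious difference is s(2q − 1). Assuming s of 0.5 to 1.0 and an SD of 1.0 to 1.5, false-positive rates at 54 per arm are 6% to 15%, 10% to 47% and 18% to 82% at 60%, 70% and 80% accuracy, and 5% at chance. The direction is the same and the size again depends on the assumptions.

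**After the change.** If total change is scored whatever its cause, then c = 1 (or s = 0) and this path adds nothing at any accuracy. Ordinary expectation bias would remain possible.

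**The case against.** **Guessing is not strictly compelled.** The protocol also uses treatment for both arms: the synopsis speaks of assigned study treatment, active or sham, and the Equipment section of sham study treatments. A rater could score change since the assigned treatment began, using anchors that mention only change. This stands as a limit: the definition is ambiguous, and only its literal reading requires a view of the arm. Nothing directs raters to the harmless reading, and raters who differ would score inconsistently. The rater instructions may settle it, but the Manual of Procedures is not among the documents.

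**The cues may be weak.** A reader might infer from the rTMS safety review ("Site pain was reported by 35.8% in active TMS group and 3.8% in the sham group") that a report of site pain nearly reveals the arm, since 0.358 / (0.358 + 0.038) = 90%. The documents do not support carrying that over. Those data come from stimulation at 120% of motor threshold. The Adverse Events section gives about 5% in the sponsor's own use, generally from coil pressure, and a coil rests on the sham participant's head too. Illustratively, 5% against the review's 3.8% gives 0.05 / 0.088 = 57%. The tapping sensation is the better-supported cue, and no document says how accurately raters would guess.

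**No such test is planned.** Correct: no CGI-I responder comparison is specified, and exploratory outcomes are to be tested according to their level of data. A reader might also infer that CGI-E will be analysed as a single ordered 16-point score; no section plans that, and the entry already sets out its two axes.

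**Clinician corroboration survives.** Also correct. CGI-S has no attribution wording and is collected at baseline and F1, so it would be wrong to infer that clinician-rated support for the PCL-5 is lost.

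**Raters are already blinded.** They are, but blinding does not remove a scoring rule that invites a guess.

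**Conclusion.** The point holds as a minor one. As worded, CGI-I lets belief about allocation into the score, and it can show an active-sham difference with no true effect if those beliefs beat chance. Across the assumptions shown, the false-positive rate runs from 6% (60% accuracy, three-quarters credit) to 90% (80% accuracy, no credit), and is 5% at chance. The top of that range requires every improver believed to be on sham to get no credit; it is an upper bound, not a forecast. A reader might take 56% or 90% as the expected error rate, but the documents give neither a guess accuracy nor a discounting rule.

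The effect is confined to CGI-I and, by the same reasoning, the therapeutic-effect axis of CGI-E. The PCL-5 analysis, its power of 0.985 and CGI-S are unaffected. The comparison that matters is at F1, because sham participants may have had open-label active treatment by F2 and F3.

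**What to change.** 1. In the CGI entry, define CGI-I as total change from baseline regardless of presumed cause.
2. At each visit, have the assessor record CGI-S and CGI-I before completing CGI-E and before reviewing side-effect questionnaire or adverse event data. This is a partial safeguard: adverse events are collected at every treatment visit and may already have been escalated to the site Investigator, and the CGI rater is not named.
3. In the Blinding section, reconcile the statement that exploratory outcomes are self-administered with the clinician-rated CGI, for example by stating that a blinded assessor rates it.

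The cost is a sentence in each of two sections, a line in the rater instructions and a fixed form order. No new data, staff or participants are needed. The change has to be in place before Stage 2 ratings begin, because ratings cannot be rescored afterwards.
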